#### 9.7.1.3 PK Evaluations

The blood samples would be assayed for SCB01A and PK parameters (maximum plasma concentration [Cmax], clearance [CL], volume of distribution [Vd], half-life [t1/2], elimination constant [Kel], mean residence time [MRT] and time to maximum concentration [Tmax]) would be determined and presented graphically and descriptively (as appropriate).

A detailed SAP would be finalized prior to final database lock. Any significant changes to the analyses described in this protocol would be addressed in the SAP and the Clinical Study Report.

### 9.7.2 Determination of Sample Size

Assumption of sample size calculation:

- Study design: Simon's two stage design
- Type I error rate (one-sided): 5%
- Power: 80%
- Response probability of null hypothesis (P0): 0.05
- Response probability of SCB01A (P1): 0.20

According to these hypotheses, up to 37 subjects need to be recruited into the study (including 10 evaluable subjects in the Stage I and 19 evaluable subjects in Stage II, with the additional 8 subjects to account for replacement of subjects those who withdraw, i.e. dropout rate is 20%). At least 4 subjects are required to achieve CR or PR after treatment with SCB01A for the study to meet its primary objective. The trial would be discontinued if no objective response is observed after the Stage I tumor assessment review.

## **9.8 CHANGES IN THE CONDUCT OF THE STUDY OR PLANNED ANALYSIS**

The statistical analysis methods have followed study protocol version 1.0, 19DEC2016, exceptions and clarifications are described below:

### PK Analysis

Pharmacokinetic sampling was bio-analyzed, and PK Parameters were calculated by Protech Pharmaservices Corporation. All PK and PK parameter data were provided to Sponsor directly, no data handling, data listing nor statistical analysis on such data would be done by A2 Healthcare.

### Objective response rate (ORR) definition

ORR is defined as the percentage of subjects who have achieved confirmed CR and PR during treatment phase, according to RECIST v1.1. Not-confirmed CR or PR, or withdrawn for DLT are counted as non-responder. There are 5 subjects who are not evaluated due to clinical disease progression or AE/SAE. Tumor non-evaluable subjects are tend to be treatment failure and would also be counted as non-responder (not evaluable for response), instead of counted as missing.

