
 • ORR is defined as the percentage of subjects who have achieved confirmed CR and PR during treatment phase, according to RECIST v1.1. Not-confirmed CR or PR, or withdraw for DLT are counted as non-responder. • PFS is defined as the time from the start of treatment up to the date of first progression based on RECIST v1.1 or the date of death, whichever comes first. • OS is defined as the time from the start of treatment up to the time that the subject is still alive. • Best overall tumor response defined as the best response from start of treatment through all treatment phase or until disease progression/recurrence. 
Survival data will be collected throughout the active treatment phase and during the 27 weeks follow-up period. Survival follow-up after subject discontinuation of treatment will be conducted every 3 weeks during the first 9 weeks, thereafter every 9 weeks until the end of the study to assess for survival. Survival rate will only be assessed in subjects with measurable disease at baseline.
 
Dose Limiting Toxicity (DLT):
 
All toxicities will be classified according to the National Cancer Institute (NCI) Common Terminology Criteria for AEs (CTCAE) version 4.03. DLT will be defined as the occurrence of any of the following criteria unless there is definitive alternative evidence that administration of SCB01A did not cause the specific toxicity:
 
 • Grade 4 neutropenia exceeding 5 days' duration; • Grade 4 thrombocytopenia; • Grade 4 anemia; • Grade 3 or greater neutropenia with complications (e.g., fever, infection etc.); • Grade 3 or greater thrombocytopenia with complications (e.g., bleeding); • Grade 3 or greater non-hematological AEs including Grade 3 unmanageable nausea and vomiting that persist for 3 or more days after drug administration. Grade 3 fatigue lasting for ≤ 1 week is not considered as a DLT; • Grade 3 or greater prolonged QTc interval; • Grade 3 or greater neurotoxicity; • Delayed treatment exceeding 14 days duration due to drug-related toxicity; • Not able to recover from grade 2 neurotoxicity exceeding 3 weeks. 
Safety measurements:
 
The following safety assessments will be done during the study:
	

Name of Sponsor/Company: SynCore Biotechnology Co. Ltd.	
Name of Study Product: SCB01A	
Protocol Number: SCB01A-22	Indication: Recurrent or metastatic squamous cell carcinoma of head and neck

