3.8.2. Early Discontinuation of Individual Subjects

The investigator may remove a subject from study treatment at his/her discretion for any of the following reasons:

- Disease progression
- Intolerable AE(s) or failure to tolerate the study treatment
- Subject decides to discontinue study therapy
- Any medically appropriate reason or significant protocol violation, in the opinion of the investigator
- Lost follow-up

Subjects may decide to discontinue study treatment for any reason. Subjects who elect to discontinue study treatment should be encouraged to continue in the study so that follow-up information on disease progression and survival status may be obtained. However, subjects may elect to withdraw consent and decline further participation in the trial.

All subjects will be followed until disease progression, withdrawal of consent, intolerable AEs/toxicity, death, loss to follow-up or the end of the study.

The investigator must determine the primary reason for a subject's discontinuation of study treatment and record this information on the CRF. Subjects who are prematurely withdrawn from study treatment are not eligible to re-initiate study treatment on this protocol at a later date.

4. Treatments

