#### 9.7.1.2 Statistical Analysis

Both ITT and PP approaches would be included in the efficacy analyses. The efficacy conclusion would be summarized according to analyses of PP population. Safety analysis would be done on ITT population. Inferential analysis results would be expressed as point estimates and their 95% confidence intervals (CIs). Analyses would be carried out using SAS® Software, version 9.4 or higher (SAS Institute, Cary, North Carolina, USA).

All time-to-event endpoints, including OS and PFS, would be reported in days (median with 95% CI and range) and calculated using Kaplan-Meier methods. Subjects who have not progressed or who have not died at the time of the analysis would be censored at the last assessment date.

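### Clinical progression without a RECIST evaluation counts against ORR but is never a PFS event on its own date, so ITT PFS can be biased upward

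*SAP*

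**What the plan says.** SAP 9.8, under the ORR definition, states: "There are 5 subjects who are not evaluated due to clinical disease progression or AE/SAE". It then gives the reason and the handling, "Tumor non-evaluable subjects are tend to be treatment failure and would also be counted as non-responder", so that they are not left as missing. SAP 9.8 opens with "The statistical analysis methods have followed study protocol version 1.0, 19DEC2016, exceptions and clarifications are described below", and the only items it then lists are PK analysis and the ORR definition.

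PFS therefore stays as in the Protocol Synopsis and Protocol 6.1, where the event is the "date of first progression based on RECIST v1.1 or the date of death, whichever comes first". SAP 9.7.1.2 gives one censoring rule for PFS and OS together: "Subjects who have not progressed or who have not died at the time of the analysis would be censored at the last assessment date". It does not say whether the assessment is a scan, a visit or a survival contact.

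No text supplied makes clinical progression a PFS event, gives a censoring date for a subject with no post-baseline tumour assessment, or plans a PFS sensitivity analysis. Protocol 3.8.2 does require the investigator to determine the primary reason for "discontinuation of study treatment and record this information on the CRF", and disease progression is one of the listed reasons.

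**The concern.** The sponsor saw that leaving these subjects as missing would flatter ORR and corrected for it. The same subjects also bear on PFS, where nothing was changed. A subject who stops for clinical progression without a RECIST evaluation can enter the PFS analysis in only two ways: censored, or counted at death if death is recorded.

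Censoring of this kind is informative, because the subject leaves the risk set on account of the failure that PFS is meant to measure. Dating the event at death overstates that subject's time without progression. The trial has no control group (Protocol 3.6), so PFS will be read in absolute terms and no comparison arm carries the same bias.

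The rest of the plan does not close the gap. The first scheduled on-treatment scan is at the end of Cycle 3, about day 64 (Protocol Table 1). An early-withdrawal scan is scheduled (Protocol 3.3), yet these 5 were still not evaluated. Follow-up collects survival status and cancer therapy without imaging (Protocol Table 3), so no later RECIST date can be expected.

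**Working it through.** **The plan's own figures.** The documents give no PFS median, event count or power, so there is no PFS figure to reproduce. The response design does reproduce: 10 then 19 subjects, continue on at least 1/10, succeed on at least 4/29, with exact one-sided type I error 0.0468 and power 0.8011. For recruitment, 29/(1 - 0.20) = 36.25, rounded up to 37. None of this depends on PFS.

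**Inputs.** k is the number of the 5 who progressed clinically; the SAP does not split them, so k is between 0 and 5. N is the number in the ITT set; the final figure is not given. I take N = 34 as an assumption, with 29 (evaluable target) and 37 (maximum recruited) as the range.

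**Route 1: censored at baseline, no later event.** Let d(t) be the number of other subjects with an event by t, with no other censoring before t. After the last of the k progressions:
- counted as events: S(t) = (N - k - d)/N
- dropped at baseline: S(t) = (N - k - d)/(N - k)
- ratio: N/(N - k)

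| N | k | N/(N - k) |
|---|---|---|
| 34 | 1 | 34/33 = 1.03 |
| 34 | 2 | 34/32 = 1.06 |
| 34 | 3 | 34/31 = 1.10 |
| 34 | 5 | 34/29 = 1.17 |
| 37 | 5 | 37/32 = 1.16 |
| 29 | 5 | 29/24 = 1.21 |

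Before the progressions the dropped version is fractionally lower, 1 - d/(N - k) against 1 - d/N. The upward bias is therefore a statement about the curve from those progressions onward.

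**Route 1 with later censoring.** If one such subject is censored at the visit where clinical progression is found, with n at risk, the ratio is n/(n - 1). With N = 34 and 8 others already progressed, n = 26 and the ratio is 26/25 = 1.04, against 34/33 = 1.03 for baseline censoring. A later censoring date changes the multiplier but does not remove the bias.

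**Route 2: counted at death.** After the last progression the curve is too high by (k/N) x P(still alive at t). Assume k = 5, N = 34, progression uniform over days 14 to 60, and exponential time to death with mean 90 days. Then P(alive at t) = (90/46)[exp(-(t - 60)/90) - exp(-(t - 14)/90)].
- Day 64: 0.749 x 5/34 = 11 points
- Day 126: 0.376 x 5/34 = 5.5 points
- Day 180: 0.206 x 5/34 = 3 points
- With k = 2, day 64: 0.749 x 2/34 = about 4 points

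**Cross-check by simulation** (N = 34, k = 5, the other 29 exponential with median 90 days, read at scans). PFS just after the first scan is 52% with the 5 as events, 61% if dropped and 63% if dated at death. The ratio 0.610/0.520 = 1.17 matches the formula.

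**Range over other assumptions** (N = 29 or 37; k = 1, 3 or 5; median 64, 90 or 126 days; clinical progression at days 21 to 50). Censoring at day 1 raises day-64 PFS by about 1 to 12 points and the median by 0 to 27 days. Dating at a death 60 or 120 days later raises day-64 PFS by about 3 to 17 points and the median by 0 to 56 days.

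**The case against.** - **No inconsistency in principle.** Non-response is not progression: stable disease and an unconfirmed PR are also non-response. A subject stopped for AE/SAE can properly be an ORR failure with no PFS event. A reader might infer that the SAP contradicts itself; it does not. What stands is narrower: for the clinical progressions, the PFS rule discards a known failure.
- **The 5 may not all be clinical progressions.** This stands. k = 5 is a ceiling, and k = 1 to 3 may be nearer the truth.
- **Never scanned, and censored at time zero?** A reader might infer both. The SAP says only that these subjects were not evaluated, and its last assessment date also governs OS, so it need not mean a scan. This stands as a limit on using N/(N - k). It does not remove the bias: on a visit or contact reading, censoring still follows from the failure, and the multiplier is no smaller.
- **Deaths will be captured.** Survival follow-up runs to at least 12 months after first treatment, so some of the 5 become events. This stands, and is why the gap fades in Route 2.
- **RECIST-or-death was prespecified.** Replacing the main PFS event now, on an open-label judgement and with these cases known, would be hard to defend. This stands and shapes the fix.
- **Best-response table.** A reader might want its CR plus PR to equal the ORR. The best-response definitions do not require confirmation and the ORR does, so the documents do not support that.
- **Other conventions may exist.** The SAP text refers to a separate detailed SAP. A censoring rule there cannot be excluded, although SAP 9.8 presents its list as the departures from the protocol.

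**Conclusion.** The concern holds for ITT PFS. On the text supplied, a clinical progression without a RECIST evaluation is either censored informatively or dated at death, and from that progression onward the curve can only be raised or left unchanged.

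The size depends on facts the SAP does not give. For baseline censoring with no later event, no other early censoring and N = 34, the multiplier is 1.03 to 1.10 for k = 1 to 3 and 1.17 for k = 5. If none of the 5 progressed clinically, there is no effect. Where deaths are recorded, the excess is largest soon after the progressions and then falls, from about 11 points at day 64 to 3 at day 180 in the k = 5 illustration.

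The consequence is limited. PFS is secondary with no test attached, and the stage rules of 1/10 and 4/29 are untouched. The efficacy conclusion rests on the per-protocol set, which under SAP 9.7.1.1 leaves out subjects with no post-baseline RECIST assessment unless they withdrew for DLT. This is a cheap improvement to the reporting of a secondary endpoint, and no reason to doubt the primary analysis.

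**What to change.** Keep RECIST v1.1 progression or death as the protocol-defined PFS. Add to SAP 9.8:

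1. An ITT PFS sensitivity analysis, reported beside the main one, in which clinical progression recorded as the reason for stopping treatment is an event on its recorded date, or on the treatment discontinuation date if no progression date was recorded. The fallback is needed because Protocol 3.8.2 requires the reason for stopping but not a date of progression.
2. A statement that subjects with no post-baseline tumour assessment who stopped for AE/SAE only, and have not died, are censored.
3. A definition of last assessment date for PFS: the last evaluable tumour assessment, or day 1 if there is none.

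Reporting how the 5 divide between clinical progression and AE/SAE would let the reader see k directly.

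The cost is a few sentences and one extra PFS run, using the recorded reason for stopping and no new data collection. The downside is that clinical progression is an open-label judgement and the analysis is added after these cases were known, so it can only be supportive. It will tend to give a less favourable PFS than the main analysis, and the difference between the two shows how much the event definition matters.
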